Pilot Study: Comparing the Effects of Hydroxychloroquine (HCQ) to Pioglitazone in Type 2 Diabetic Patients Failing Maximal Doses of Metformin Plus a Sulfonylurea

ClinicalTrials.gov NCT02303405

Protocol

Last Modified: January 11, 2017

Pilot Study: Comparing the Effects of Hydroxychloroquine (HCQ) to Pioglitazone in Type 2 Diabetic Patients Failing Maximal Doses of Metformin Plus a Sulfonylurea

Background: Type 2 diabetes is characterized by insulin resistance (decreased insulin sensitivity), as well as an increased inflammatory state. It is unclear whether insulin resistance causes the inflammatory state, whether the inflammatory causes the insulin resistance, or whether each is independent of the other (Shoelson SE et al, J Clin Invest 2006; 116:1793-1801). The LA County DHS formulary for treating type 2 diabetes is currently limited to metformin, two sulfonylurea agents (SU), pioglitazone (a thiazolidinedione, or TZD) and insulin. The treatment algorithms utilized in the Diabetes Programs at the Martin Luther King Jr. Outpatient Center (MLK) and the South Central Family Health Center (SCFHC) start with metformin, after which an SU is added, and if maximum doses of both do not control patients, a maximum dose of pioglitazone is then added. We have previously published our experience with TZDs (both rosiglitazone and pioglitazone) as the third drug and found that TZDs lower HbA_{1c} levels approximately 2.0% (from a baseline value of 9.3-9.5%) with two-thirds of our patients meeting our target of <7.5% after 4 months, which avoids starting insulin at that time (Tran MT, et al. Diabetes Care 2006; 29:1395-1396). As long as HbA_{1c} levels can be maintained <7.5%, insulin is not necessary according to the treatment algorithms in the Diabetes Program at MLK-MACC. Unfortunately, although they reduce insulin resistance, TZDs may be prone to side effects including fluid retention, heart failure, weight gain, and decreased bone mineral density leading to increased fracture risk in susceptible individuals.

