Secondary Outcomes: To collect preliminary data to eventually compare a) the percentage of patients who achieve HbA_{1c} <7.5% after receiving either HCQ or PIO for 4 months; b) the effect of PIO vs. HCQ in lowering fasting plasma glucose (FPG) and weight; and c) the effects of HCQ vs. PIO on inflammation and insulin resistance.

Research Design: A 4-month, randomized, prospective, open-label comparison trial

Subjects: Type 2 diabetic patients inadequately controlled on maximally tolerated doses of metformin plus a SU.

Recruitment: Subjects will be recruited from the Diabetes Programs at MLK and South Central Family Health Center (SCFHC). These centers serve the same large population of low-socioeconomic status and low-educational level ethnic minority patients living in the south and south-central region of Los Angeles. The diabetes clinic at MLK is staffed by the faculty of the Endocrinology Division of Charles R. Drew University of Medicine and Science, and the diabetes care providers at the SCFHC clinic were trained on the same treatment protocols by the study co-investigator. This study protocol will be reviewed by the Institutional Review Board of Charles R. Drew University prior to study initiation, and an IND application will be submitted to the FDA.

Inclusion Criteria:

- Male or female, age 18-75, inclusive
- Known type 2 diabetes (diagnosed according to 1997 ADA diagnostic criteria) receiving diabetes treatment at MLK or SCFHC
- At least 3 months of treatment with maximum tolerated doses of metformin *and* a SU, *and* inadequate glycemic control (HbA_{1c} ≥ 7.5% and < 11.0%)
- Body mass index (BMI) < 45 kg/m²
- Able to comply with all scheduled visits and requirements of the protocol

Exclusion Criteria:

- Any contraindications to the use of metformin or a SU
- Extreme hyperglycemia (FPG ≥ 300 mg/dL), symptoms of polyuria or polydipsia, or HbA_{1c} ≥ 11.0%
- Current use of insulin; history or clinical suspicion of type 1 diabetes mellitus
- Symptomatic hypoglycemia occurring at an average frequency > once per day
- Highly erratic dietary schedules, extremely food insecure households, or homelessness that may adversely affect good glycemic control, as judged by the investigators
- Occupations that involve regular operation of motor vehicles or other heavy machinery that may pose a hazard in the event of unanticipated blurred vision

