Laboratory Measurements: All laboratory analyses except fasting insulin and hsCRP will be obtained by the respective clinic phlebotomists specified above, and conducted by the respective clinical laboratories specified above, or the CTRC. Samples for insulin and hsCRP levels will be obtained at the CTRC, banked, and will be measured in the future by the CTRC Core Lab using commercially available RIA and/or ELISA kits: Millipore HI-14K Human Insulin RIA (Millipore, Billerica, MA); MP Biomedicals 07BC-1119 ultrasensitive CRP ELISA (MP Biochemicals, Orangeburg, NY); samples for insulin and hsCRP will remain frozen until assay reagents are available for batched runs once all samples have been collected.

Statistical Analyses:

All data will be collected onto Excel spreadsheets. Non-normal data will be log-transformed, as appropriate.

Intended Primary Endpoint: *The between-group change in the HbA_{1c} level from baseline to 4 months.*

Intended Secondary Endpoints:

A) The between-group difference in the change by 4 months of: i) % of subjects achieving HbA_{1c} $< 7.5\%$, ii) FPG, iii) weight and BMI, iv) HOMA-IR and QUICKI, and v) hsCRP and leukocyte counts;

B) For each group, the within-group change by 4 months in HbA_{1c}, FPG, weight and BMI, HOMA-IR and QUICKI, hsCRP, and leukocyte counts;

C) The between-group difference in the incidence of i) all hypoglycemic events, ii) severe hypoglycemic events, and iii) all adverse events excluding hypoglycemia.

Analysis: Changes in all continuous outcome measures will be compared between groups using 2-way repeated measures ANOVA. A chi-square analysis will be used to compare the percent of subjects achieving HbA_{1c} $< 7.5\%$ between groups. Changes within groups between baseline and

4-months will be made with one-way ANOVA. We will plan to eventually conduct both an intent-to-treat (ITT) analysis (missing data imputed using last-observation carried forward) as well as a secondary analysis of only those completed subjects with mean medication compliance $\geq 90\%$.

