Sample Size Calculations: Due to limited available funding, as of late 2015, this pilot study alone will be unable to enroll the needed number of subjects to meet the originally intended level of statistical power; available funding accommodates enrollment of up to 60 subjects. However, the partial data obtainable using the available funding will still provide preliminary information as to a) the possibility of efficacy that may at least be similar between HCQ and PIO; b) the possibility of potentially similar effects of HCQ and PIO on secondary measures such as weight, inflammation, and insulin resistance; and c) the presence or possibility of any clinically significant safety concerns with HCQ in comparison to PIO that may be relevant to the eventual clinical use of HCQ for diabetes, or the value of pursuing future funding to complete the intended full enrollment to fully meet the study objectives. This pilot study will therefore still provide valuable preliminary data that will be critical towards eventually securing additional funding to continue the study and ultimately achieve the total enrollment target so as to draw the intended conclusions.

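### The comparison of the percent reaching HbA1c <7.5% is valid but takes no account of baseline HbA1c; a prespecified baseline-adjusted analysis would probably add a little precision at almost no cost.

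*Combined protocol and SAP*

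**What the plan says.** - **Endpoint.** The target is item A(i) of the intended secondary endpoints: "The between-group difference in the change by 4 months of: i) % of subjects achieving" HbA1c <7.5%. It is also the first secondary outcome listed near the front of the protocol. The primary endpoint is the change in HbA1c itself.
- **Analysis.** Statistical Analyses: "A chi-square analysis will be used to compare the percent of subjects achieving" the target. No section adds a covariate or a stratified version. Continuous outcomes are treated differently: "Changes in all continuous outcome measures will be compared between groups using 2-way repeated measures ANOVA", so baseline enters there as one of the repeated measures.
- **Entry range.** Inclusion Criteria define "inadequate glycemic control" as HbA1c "≥ 7.5% and < 11.0" percent, so every subject enters above the target.
- **Allocation.** Study Medication allocates by odd or even medical record number, with no stratification by HbA1c or clinic.
- **Prior experience.** Background reports that thiazolidinediones lowered HbA1c by "approximately 2.0% (from a baseline value of 9.3-9.5" percent), with "two-thirds of our patients meeting our target of <7.5% after 4 months". It gives no SD and no relation between baseline and response.
- **Size.** Sample Size Calculations: "available funding accommodates enrollment of up to 60 subjects". The study is described as short of its intended power, and its data as preliminary.

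**The concern.** The fall needed to reach the target depends on where the subject starts: just over 0.1 point from 7.6%, and more than 3.4 points from 10.9%. Baseline HbA1c is therefore a natural prognostic variable for this endpoint, and it is measured at no extra cost. A chi-square discards it.

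Two things are at stake. The first is precision, in a trial whose size is capped by funding and cannot be increased to compensate. The second is how to read the single result obtained: if one arm happens to start lower, its responder percentage is raised for a reason unrelated to the drug. The result is meant to inform a funding case, and 7.5% is the programme's threshold for avoiding insulin, so the estimate is likely to be read at face value.

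**Working it through.** The plan gives no alpha, power, SD or expected HCQ rate for this endpoint, so there is no figure to reproduce. Assumed throughout: 30 per arm (60 split equally) and two-sided 0.05.

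**1. Where the cut falls.** Background's own figures put the mean 4-month value at 9.3 − 2.0 = 7.3 to 9.5 − 2.0 = 7.5, right at the target. Small shifts in HbA1c move the responder percentage most in that region.

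**2. Precision of the planned test.** With the two-thirds rate in both arms, SE = √(2 × 2/3 × 1/3 ÷ 30) = 0.122, or about 12 percentage points. Chi-square power is 0.26 for 2/3 vs 0.50, 0.55 for 2/3 vs 0.40, and 0.75 for 2/3 vs 1/3.

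**3. How often baseline is unbalanced.** The SD of the between-arm difference in mean baseline is s × √(2/30). Assume a baseline mean of 9.1 and SD of 0.85.
- If 0.85 is the SD before truncation to 7.5-11.0, the limits lie at −1.88 and +2.24 SD. The realised SD is 0.85 × √(1 − 0.210 − 0.001) = 0.755. Then 0.755 × 0.258 = 0.195, and P(|difference| > 0.3) = 2[1 − Φ(0.3/0.195)] = 0.12.
- If 0.85 is the realised SD: 0.85 × 0.258 = 0.219, and P = 2[1 − Φ(0.3/0.219)] = 0.17.

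**4. Linear model.** Week 16 = 7.2 + slope × (baseline − 9) + error, with no arm effect, slope 0.3-0.7 and residual SD 0.8-1.0 (all assumed).
- P(target) = Φ([0.3 − slope × (baseline − 9)] ÷ residual SD). From 7.6% this is Φ(0.72/1.0) = 0.76 to Φ(1.28/0.8) = 0.95. From 10.9% it is Φ(−1.03/0.8) = 0.10 to Φ(−0.27/1.0) = 0.39.
- Simulated variance of the risk difference, unadjusted over adjusted: about 1.01-1.22. The ends carry simulation error of a few hundredths.
- Shift in the unadjusted difference per 0.1-point imbalance: 1.1-2.9 percentage points. At 0.3 points: 3 × 1.1 = 3.3 to 3 × 2.9 = 8.7, so about 3-9. The adjusted difference shifts by about 0.

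**5. Logistic model, as a second check.** Baseline was truncated normal centred at 9.4 with realised SD 0.73-0.89. Odds of response fell by the stated factor per 1-point higher baseline. The PIO rate was 2/3; the HCQ rate was 2/3 under the null and 1/3 under the alternative. There were 20,000 trials per setting.

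| Odds factor per point | Variance change with adjustment | Power, chi-square | Power, adjusted | Null rejection when imbalance >1.5 SD: chi-square |
|---|---|---|---|---|
| 1 (not prognostic) | about +2% | 0.76 | 0.76 | 0.05-0.06 |
| 1.5 | about −1% | 0.75 | 0.76-0.77 | 0.05 |
| 2 | −3 to −6% | 0.76 | 0.78-0.79 | 0.06-0.07 |
| 3 | −10 to −16% | 0.76 | 0.81-0.83 | 0.08-0.10 |
| 5 | −19 to −27% | 0.75-0.76 | 0.85-0.88 | 0.11-0.14 |

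In the same unbalanced trials the adjusted test rejects at 0.05-0.065. Over all trials the chi-square type I error is 0.044-0.050 in every setting. The mean risk difference is 0.00 under the null and −0.33 under the alternative, with or without adjustment. The adjusted likelihood-ratio test rejects at 0.054-0.060 under the null, so its power gains are slightly overstated.

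**The case against.** The strongest reply is that nothing is wrong with the planned test. It is valid, and its standard error already covers the variability from chance imbalance. A reader might infer that chance imbalance biases the result. That is not so: if allocation acts as random, the unadjusted difference is right on average and the test holds its level. Only the estimate conditional on the imbalance actually seen is shifted, and a shift of 3-9 points is smaller than the 12-point standard error. This part of the reply stands.

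A reader might also infer that baseline HbA1c largely determines who reaches the target. The documents give no figure for that. In the logistic settings where baseline is prognostic, it explains 2-28% of the variance in response, well under half. Setting the 3.4-point fall needed from 10.9% against a flat 2.0-point effect also misleads, because 2.0 is a mean fall from 9.3-9.5%. In the linear model the mean fall from 10.9% is 3.7 − 1.9 × slope, or 2.4-3.1 points, and 10-39% of such subjects still reach the target. This part stands too.

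Finally, the endpoint is secondary in a pilot that says it is underpowered, and adjustment brings a model into small samples. That limits the weight of the point but does not remove it. The covariate is already collected, and the worst simulated cost, when baseline is not prognostic at all, is about 2% in variance.

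**Conclusion.** The point holds as a minor efficiency improvement. The chi-square is valid and unbiased over repeated randomisation. It is probably less efficient than a baseline-adjusted analysis, by a variance factor of about 1.01-1.22 under the assumed linear model, and it leaves the observed difference open to a shift of about 3-9 percentage points at a 0.3-point imbalance.

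That the analysis is unadjusted and the allocation unstratified is certain from the text. The size of the gain is not: it rests on assumed slopes, residual SD, baseline SD and equal arms, and it is negligible if baseline is weakly prognostic. The point does not carry over to the primary endpoint, where baseline enters as a repeated measure.

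Allocation by record number in an open-label trial is predictable and could produce systematic rather than chance imbalance. That is a separate matter, and adjustment would remove only the part carried by baseline HbA1c.

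**What to change.** In the Analysis paragraph, name as the main analysis of the HbA1c <7.5% endpoint a logistic regression on treatment arm and continuous baseline HbA1c. Report the standardised risk difference (each subject's predicted probability under each arm, averaged over all subjects) with a 95% CI. Keep the chi-square or Fisher test as supportive, and state in advance that a Firth penalty will be used if cells are sparse. Fixing this before analysis also prevents a later choice between adjusted and unadjusted results in an open-label trial.

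The cost is a change of wording only, with no new data or visits. The downsides are slightly more modelling and a likelihood-ratio test that may be slightly liberal at this size, so the emphasis should be on the estimate and its interval.

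### Within-group change from baseline to 4 months (secondary endpoint B) is assigned a one-way ANOVA, which as written ignores the pairing; a paired analysis should be named

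*Combined protocol and SAP*

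**What the plan says.** Under Intended Secondary Endpoints, item B is defined as "For each group, the within-group change by 4 months in" HbA1c, FPG, weight and BMI, HOMA-IR and QUICKI, hsCRP and leukocyte counts. The Schedule of Procedures has the same patients measured at baseline, 2 and 4 months.

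The Analysis paragraph gives two rules for continuous outcomes:

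- Between groups, changes are "compared between groups using 2-way repeated measures ANOVA".
- Within groups, the sentence opens "Changes within groups between baseline and" and ends "4-months will be made with one-way ANOVA".

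The repeated measures qualifier appears in the first rule and not in the second. Nothing else in the document names a paired t-test, a subject factor or an analysis of change scores for endpoint B. The only other general rule is "Non-normal data will be log-transformed, as appropriate".

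**The concern.** A one-way ANOVA with visit as its factor and two levels is the unpaired two-sample t-test. It treats a patient's baseline and 4-month values as if they came from different people, so variation between patients stays in the error term. If the two values are positively correlated, standard errors are too large, confidence intervals too wide and the test too conservative.

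This touches readings the Background section intends to make. It says HCQ may be useful even if less effective than PIO, provided it significantly lowers HbA1c. It would also take a lack of improvement in insulin sensitivity on HCQ as evidence against a role for inflammation. With no untreated arm, endpoint B in the HCQ group is the planned test of change under HCQ, and a test that has thrown away precision leans towards finding no change. The same section warns that "TZDs may be prone to side effects including fluid retention, heart failure, weight gain" and other effects, and weight is the outcome where ignoring the pairing is likely to cost most. The Sample Size Calculations section already concedes that the intended power cannot be reached.

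**Working it through.** The plan states no power, SD or alpha for this endpoint, so there is no figure of its own to reproduce.

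**Inputs**

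- Patients per arm: n = 30. The Sample Size Calculations section says "available funding accommodates enrollment of up to 60 subjects"; an even split is assumed.
- Two-sided alpha 0.05: assumed.
- HbA1c SD 1.0 at baseline (s0) and 1.3 at 4 months (s1), correlation r of 0.3, 0.5 or 0.7: assumed.
- Weight SD 15 or 20 kg at both visits, r of 0.95, 0.97 or 0.99: assumed.

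**Formulas**

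- Unpaired (literal one-way ANOVA): SE = √[(s0² + s1²)/n], with 2n − 2 = 58 df and critical t = 2.002.
- Paired: SE = √[(s0² + s1² − 2·r·s0·s1)/n], with n − 1 = 29 df and critical t = 2.045.
- With equal SDs the ratio of the two SEs is 1/√(1 − r).

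**HbA1c**

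Unpaired: SE = √[(1.00 + 1.69)/30] = 0.299, and 95% CI half-width = 2.002 × 0.299 = 0.60 at every correlation.

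Paired, r = 0.5: SE = √[(2.69 − 1.30)/30] = 0.215, half-width = 2.045 × 0.215 = 0.44, SE ratio = 0.299/0.215 = 1.39.

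Type I error and power come from simulating bivariate normal pairs, with both standard errors estimated in each simulated trial. Power is given as unpaired v paired.

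| | r = 0.3 | r = 0.5 | r = 0.7 |
|---|---|---|---|
| SE ratio | 1.19 | 1.39 | 1.76 |
| Paired half-width (unpaired 0.60) | 0.52 | 0.44 | 0.35 |
| True type I error, unpaired | 0.021 | 0.008 | 0.001 |
| Power, 0.5-point fall | 36% v 48% | 34% v 61% | 30% v 81% |
| Power, 1.0-point fall | 94% v 97% | 96% v 99% | 99% v nearly 100% |
| Power, 1.0-point fall, n = 20 | 79% v 87% | 83% v 95% | 87% v 99.5% |

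For falls of 1.5 points or more, both tests have essentially 100% power at n = 30. That covers the fall of about 2.0 points that the Background section reports for TZDs.

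**Weight**

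Unpaired: SE = 15 × √(2/30) = 3.87 kg or 20 × √(2/30) = 5.16 kg; half-widths 7.8 and 10.3 kg.

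Paired, narrowest case (SD 15, r = 0.99): SE = 15 × √(0.02/30) = 0.387 kg, half-width 0.8 kg. Widest case (SD 20, r = 0.95): SE = 20 × √(0.10/30) = 1.155 kg, half-width 2.4 kg.

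SE ratio: 1/√0.05 = 4.5 up to 1/√0.01 = 10.

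Simulated power for a 3-kg change: at most 0.01% unpaired. Paired, at r = 0.95/0.97/0.99, it is 92%/99%/100% with SD 15 and 71%/90%/nearly 100% with SD 20.

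**The case against.** **It may be shorthand.** Going from a two-way to a one-way ANOVA drops the group factor and leaves time, on the same patients, and both sentences speak of changes. The authors may simply have left out the words repeated measures. That is plausible, but an analyst who follows the text would run the unpaired test, and nothing else in the document corrects it.

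**The correlation may be low.** Entry is restricted to HbA1c of at least 7.5% and below 11.0%, and restricting the range tends to lower the correlation with follow-up. At r = 0, 0.1 and 0.2, with the same SDs and n = 30, the SE ratio is 1.00, 1.05 and 1.11. Power for a 0.5-point fall is then 38%, 37% and 36% unpaired against 37%, 40% and 44% paired. This stands: the loss for HbA1c could be small. At r = 0 the unpaired test even has a slight edge from its larger df, and a negative correlation would reverse the direction. But positive correlation is the ordinary expectation for these measures, last observation carried forward raises it where baseline values are carried, and the low-correlation cases shrink only the HbA1c loss.

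**Weight is tested elsewhere.** Endpoint A(iii) compares weight and BMI between groups by repeated measures ANOVA, so the randomised weight comparison keeps the within-patient information. This also stands. What is lost is the estimate of weight change within each arm.

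**It is a conservative error on a secondary endpoint in a pilot.** That is correct and limits the seriousness. It does not make the named test suitable.

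**Conclusion.** The concern holds. As written, the plan prescribes an unpaired test for paired data on all the outcomes in endpoint B. Given positive within-patient correlation, precision and power are lost; false positives are not created. The primary comparison and the between-group secondary comparisons are unaffected.

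The size varies by outcome. For HbA1c it is moderate for small changes and negligible for falls of 1.5 points or more. For weight and BMI it is likely to be severe. All these figures depend on the assumed SDs, correlations, alpha and even split; the document fixes only the enrolment cap of 60. The wording should be corrected before analysis, but this is not a flaw that threatens the trial's main aim.

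**What to change.** Replace the within-group sentence in the Analysis paragraph with wording such as:

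> *Within-group changes from baseline to 4 months will be analysed with a paired t-test (equivalently, one-way repeated measures ANOVA with subject as a factor), on the log scale where log-transformation is planned, and reported as mean change with 95% CI. Because there is no untreated control, within-group changes are descriptive.*

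For log-transformed outcomes, the mean change should be back-transformed and reported as a ratio of 4-month to baseline value. The last sentence of the wording is a caution on interpretation; the correction of the test does not depend on it. If it is adopted, the Background statement about HCQ significantly lowering HbA1c should be read in the same light.

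The cost is one sentence of analysis-plan text. The data, visits and sample size stay the same.
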